Intraoperative critical events can have multiple risk factors and contribute to anaesthesia related complications. The incidence ranges from 2.32% to 11.7% and shows significant variability among different settings. The largest intraoperative critical event study in Europe showed a high number of intraoperative severe critical events (5.2%) with significant variability between hospitals. Respiratory critical events were the most common (3.1%) followed by cardiovascular instability (1.9%). The immediate poor outcome was 5.4%. (6)

There are specific considerations that should be sought in Paediatric population anaesthesia related critical events. These may include the choice of drug and their response. Additionally, the anaesthesia related adverse effects may have long term sequelae for children. As a result, studying those critical events will help to identify the factors related and final outcomes which will help in standardizing the care. It will also be a base to advocate for intraoperative care.

Reported incidences from high income countries

Studies from Europe reported incidences ranging from 0.14% for serious adverse events to 3.4% for critical incidents. (7) Similarly a study done by Cohen et al showed a severe anaesthesia critical event rate of 1.4 per 1000. The commonest events were respiratory followed by cardiac. (8) A large international multicentric cohort study covering North America, Oceania and Europe reported an incidence of 24 % for intraoperative adverse events. (9)

Reported incidences from low- and middle-income countries

The reported incidences for critical events vary across low and middle-income countries (LMICs). A South Korean study reported a 0.4% incidence of paediatric anaesthesia related critical incidents, with respiratory events been the commonest (55% of the cases), (10) compared to an Indian study which reported a 12% incidence, predominated by respiratory complications. (11) Generally, LMICs may carry at least double the burden of intraoperative critical events to high-income countries, although the risk should be similar to that of HICs. These excess events should be preventable. (12)

Types of complications

Respiratory related complications are most commonly reported, followed by cardiovascular events.

Risks associated with complications

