The following patient and surgical risk factors have been shown to contribute to intraoperative critical events: age <1 year, ASA physical status III and IV, urgency of the surgical procedure, and preexisting comorbidities. The level of training of the anaesthesia providers and the number of years of experience, as well as the type of anaesthesia and surgery done are potentially important risk factors. (13)

Study rationale

African Surgical Outcomes Study in Paediatric patients (ASOS-Paeds) determined the incidence of in-hospital postoperative complications up to 30 days after surgery in paediatric surgical patients across different hospitals in Africa. This study will evaluate the intra-operative critical incidents reported in ASOS-Paeds. It is hoped that these findings will contribute to improving perioperative care for paediatric surgical patients in Africa.

Aims and objectives of the “severe critical incidents” analysis

Aims

The aims of this study are to describe the incidence of intraoperative severe critical events, the types of severe critical events, and risk factors independently associated with severe critical events.

Objectives of the study

Primary objective

1. To describe the incidence of intra-operative severe critical events in paediatric surgical patients in Africa

Secondary objectives

1. To describe the categories and types of severe critical events
2. To identify risk factors independently associated with severe critical events

Sensitivity analyses

1. Two sensitivity analyses will be conducted:
 - a. The sensitivity analyses of elective surgical patients, and emergency surgical patients, and
 - b. A sensitivity analysis excluding the two countries providing more than 10% of the patients to the dataset (Egypt and South Africa)

Statistical Analysis Plan

A) Data Validation

- Report on the number of incomplete data points
- Report on primary outcome data
 - % missing data for incidence of severe critical events
- Provide STROBE diagram of recruited patients

B) Statistical tests

- Categorical variables will be described as number and proportions (percentage) and will be compared using appropriate Chi-squared or Fisher's exact tests.
- Continuous variables will be calculated and reported as mean and standard deviation (SD) if normally distributed, or median and inter-quartile range (IQR) if not normally distributed.

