- Comparisons of continuous variables between groups will be performed using t-tests, one-way ANOVA or equivalent non-parametric tests as appropriate.
- If $< 5\%$ of data are missing for the primary outcomes, a complete case analysis will be conducted
- A p-value of less than 0.05 will be considered statistically significant for all analyses
- Generalized mixed effects model analysis will be performed for exploration of candidate variables for prediction of risks for the primary outcome i.e. incidence of severe critical events
 - Further description to follow in the section discussing risk prediction
- Sensitivity analyses will be conducted.

C) Primary objective

1. To describe the incidence of intra-operative severe critical events in paediatric surgical patients in Africa

This will be presented as number (n/N), percentage (%)

The cohort will be described according to the variables (Table 1)

- Age, ASA PS, sex
- Comorbidities
- Describe the Hospital, Surgery and Anaesthesia information
 - Hospital level
 - Urgency of surgery (elective, emergency)
 - Severity of surgery (minor, intermediate, severe),
 - Indication for surgery
 - Type of surgery
 - Intraoperative factors
 - Most senior anaesthetist
 - Most senior surgeon

- Time of induction

D) Secondary objectives

1. To describe the categories and type of intra-operative severe critical events
 - Outcome definitions are defined in the study protocol
 - The categories of severe critical events will be presented as airway, respiratory, cardiovascular, metabolic, and other severe critical events categories (Table 2) using % to indicate the incidence (number of patients with severe critical events divided by the number of patients) and 95% confidence intervals.
 - To describe the types of severe critical events within each category
 - The categories and types of severe critical events will also be presented by the level of facility, and the level of the anesthesia providers (Table S1)
2. To identify risk factors independently associated with severe critical events
 - All variables will be entered into the model, unless there are less than 10 events per variable. If this is the case, risk factors with a p value ≤ 0.05 for severe critical events identified by univariate analysis will be entered into the model. (Table 3) The reference category for the surgical discipline will be decided by the surgical discipline with the lowest incidence of severe critical events

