 - Results will be presented as unadjusted and adjusted odds ratios (ORs) with 95% confidence intervals (CI's).

Analyses will be conducted using Statistical Package for the Social Sciences (SPSS) version 30 (SPSS Inc., Chicago, IL, USA) and R: A language and environment for statistical computing. Vienna, Austria: R Foundation for Statistical Computing (2024) using Studio: Integrated Development Environment for R. Boston, MA: RStudio, Inc. (2024).

Tables

Table 1. Description of cohort including patient, surgical, anaesthesia and facility characteristics

		All patients (n=)	Patients with severe critical events (n=)	Patients without severe critical events (n=)
		n/N (%)	n/N (%)	n/N (%)
Age	Mean (SD) Median (IQR)			
Sex				
Male				
Female				
Age categories				
0-28 days				
29 days to < 1 yr				
1 to < 4 yr				
4 to < 13 yr				
13 to <18 yr				
ASA PS				
I				
II				
III				
IV-V				
Urgency of surgery				
Routine				
Emergency				
Severity of surgery				
Minor				
Intermediate				
Major				
Primary indication for surgery				
Non-communicable disease				
Infective				
Trauma				
Congenital				
Hospital level				
First				
Second				
Third				
Most senior anaesthetist				

Specialist			
Non-specialist physician			
Nurse			
Non-physician			
Most senior surgeon			
Specialist			
Non-specialist physician			
Nurse			
Non-physician			
Type of surgery			
Orthopaedic			
Cardiac			
ENT			
Gynaecological			
Hepatobiliary			
Kidney/urological			
Gastrointestinal			
Thoracic			
Ophthalmology			
Maxillo-facial/ dental			
Plastic/cutaneous			
Neurosurgery			
Burns			
Comorbidities			
Cardiac disease			
Chronic respiratory disease			
Neurological disorder			
HIV/AIDS			
Cancer			
Current respiratory tract infection			
Intraoperative factors			
Duration			
Surgical checklist used			
Time			
Daytime			
After hours			

Table 2: The categories and types of intra-operative severe critical events

	Overall	Incidence
	n/N (%)	% (95% CI)
Categories of anaesthetic severe critical incidents		
Any		
Any Airway/respiratory		
Any CVS		
Any Other		
Types of severe critical events by category		
Airway/respiratory		
Difficult BMV		
Difficult Intubation		
Failed Intubation		
Laryngospasm		
Bronchospasm		
Aspiration		
Severe Hypoxia		
CVS		
Bradycardia		
Cardiovascular instability		
Cardiac Arrest		
Metabolic		
Temp < 36		
Low Glucose		
Other		
Anaphylaxis		
Drug error		
Death		
Yes		
No		

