Table 3. Univariable and multivariable analysis of preoperative factors associated with intra-operative severe critical events

	Univariable		Multivariable	
	OR (95% CI)	p-value	OR (95% CI)	p-value
Age (per 1 year)				
Sex				
Male				
Female	Reference			
ASA PS				
I	Reference			
II				
III				
IV-V				
Urgency of surgery				
Routine	Reference			
Emergency				
Severity of surgery				
Minor	Reference			
Intermediate				
Major				
Primary indication for surgery				
Non-communicable disease	Reference			
Infective				
Trauma				
Congenital				
Hospital level				
First				
Second				
Third	Reference			
Most senior surgeon				
Specialist	Reference			
Non-specialist physician				
Nurse				
Non-physician				
Most senior anaesthetist				
Specialist	Reference			

Non-specialist physician				
Nurse				
Non-physician				
Type of surgery				
Orthopaedic				
Cardiac				
ENT				
Gynaecological				
Hepatobiliary				
Kidney/urological				
Gastrointestinal				
Thoracic				
Ophthalmology				
Maxillo-facial/dental				
Plastic/cutaneous				
Neurosurgery				
Burns				
Comorbidities				
Cardiac disease				
Chronic respiratory disease				
Neurological disorder				
HIV/AIDS				
Cancer				
Current respiratory tract infection				
Intraoperative factors				
Duration				
Surgical checklist used	Reference			
Surgical checklist not used				
Time				
Daytime	Reference			
After hours				

Table S1: Intra-operative severe critical events by facility and anaesthesia provider

	Hospital level			Most senior anaesthetist			
	District	Regional	Tertiary	Specialist	Non-specialist physician	Nurse	Non-physician
Categories of anaesthetic severe critical incidents							
Any							
Any Airway/respiratory							
Any CVS							
Any Other							
Types of severe critical events by category							
Airway/respiratory							
Difficult BMV							
Difficult Intubation							
Failed Intubation							
Laryngospasm							
Bronchospasm							
Aspiration							
Severe Hypoxia							
CVS							
Bradycardia							
Cardiovascular instability							

Cardiac Arrest							
Metabolic							
Temp < 36							
Low Glucose							
Other							
Anaphylaxis							
Drug error							
Death							
Yes							
No							

References

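### Choosing the reference surgical discipline by its low event rate inflates the 12 discipline odds ratios together and can leave them resting on a small or event-free group

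*SAP*

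**What the plan says.** Under D) Secondary objectives, item 2, the SAP sets the reference for type of surgery from the results: "The reference category for the surgical discipline will be decided by the surgical discipline with the lowest incidence of severe critical events". In Table 3 the block headed "Type of surgery" lists 13 disciplines, none marked as reference. Every other factor with several levels in that table has a named one (for example ASA PS I, minor surgery, third-level hospital, specialist).

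The reporting and testing rules that then apply to these contrasts are: "Results will be presented as unadjusted and adjusted odds ratios (ORs) with 95% confidence intervals" and "A p-value of less than 0.05 will be considered statistically significant for all analyses". No multiplicity adjustment, minimum size for the reference, or rule for a discipline without events is given.

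Two sets of sensitivity analyses are planned: "The sensitivity analyses of elective surgical patients, and emergency surgical patients" and "A sensitivity analysis excluding the two countries providing more than 10% of the patients to the dataset". The SAP does not say whether the reference discipline is carried over from the full cohort or chosen again.

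**The concern.** Fixing the rule in advance does not make it independent of the data. It selects the minimum of 13 noisy rates, and that minimum is on average below the selected discipline's true rate. All 12 contrasts share this denominator, so they err in the same direction. From ordinary 2×2 tables, every unadjusted odds ratio is at least 1 by construction. Adjusted ones move the same way, although some fall below 1.

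Small disciplines have the noisiest rates and so are picked often. That widens all 12 intervals at once. If the selected discipline has no events, no discipline odds ratio can be estimated by maximum likelihood. If the rule is re-applied in the subsets, a change in the odds ratios may reflect only a change of comparator.

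At stake is the reading of 12 of the 40 odds ratios that answer secondary objective 2. They could look like raised risks, or be too imprecise to read, because of the selection rule alone.

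**Working it through.** The plan gives no discipline odds ratio or power figure to reproduce, so the rule itself was simulated.

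**Inputs from the documents**
- 7000 patients (protocol, Summary). Protocol section 5.10 says there is no specific sample size, so this is a working figure.
- Event rates of 2.32% and 11.7% (SAP, Introduction: "The incidence ranges from 2.32% to 11.7% and shows significant variability among different settings") and 5.2% (the large European study cited there).
- 13 disciplines, hence 12 odds ratios. Table 3 in row order: 1+1+3+1+2+3+2+3+3+12+6+1+1+1 = 40.

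**Assumptions: discipline sizes**
- Equal: about 7000/13 = 538 each.
- Uneven A: 1540, 1120, 910, 770, 630, 490, 420, 350, 280, 210, 140, 70, 70.
- Uneven B: as A, but the last four are 280, 70, 70, 70.

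**Method.** For each scenario, 20,000 cohorts with binomial events per discipline. The reference is the lowest observed rate (ties broken at random), compared with the largest discipline as fixed reference. Wald 95% intervals were used on the log odds ratio; summaries use estimable odds ratios. The true odds ratio is 1 in steps 1 to 3.

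**1. Unadjusted, no true differences** (at 2.32% / 5.2% / 11.7%)

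| Sizes | Median OR, SAP rule | Median OR, largest as reference |
|---|---|---|
| Equal | 1.81 / 1.45 / 1.28 | 1.00 |
| Uneven A and B | 1.95–2.03 / 1.85–1.91 / 1.50–1.54 | 0.99–1.01 |

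- Equal sizes: intervals miss the true value in 16–18% of contrasts, against 4–5% with a fixed reference. At least one discipline is falsely significant in 70–75% of studies, against 29–31%.
- Uneven sizes: false positives do not rise consistently (23–46% against 35–41%), because the intervals are wide. Non-coverage is 6–11%.

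**2. Small or event-free reference (uneven sizes)**
- The reference has 140 patients or fewer in 59–66% of studies.
- At 5.2% the median standard error of the log odds ratio is 0.62–0.73, against 0.26. The interval is the estimate divided and multiplied by exp(1.96 × SE): exp(1.96 × 0.62) = 3.4 and exp(1.96 × 0.73) = 4.2, against exp(1.96 × 0.26) = 1.7.
- Chance that some discipline has no events, which then becomes the reference: 1 − ∏(1 − (1 − p)^n). For one discipline of 70 at 2.32%, 0.9768^70 = 0.193. Two such disciplines alone give 1 − (1 − 0.193)² = 0.35, and all 13 in mix A give 37.9%.
- Results at the three rates: A 37.9% / 4.8% / 0.03%; B 47.7% / 7.0% / 0.05%. With equal sizes the chance is essentially zero.

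**3. Adjusted for ASA class and urgency** (300 simulations per scenario, uneven mix A, no hospital effect). Median odds ratio 1.21–1.79 (equal) and 1.41–2.06 (uneven), against 0.97–1.02 with a fixed reference. Between 1% and 12% of adjusted odds ratios fall below 1.

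**4. True risks differ** (reported OR divided by true OR; uneven = mix A)
- Standard deviation 0.3–0.5 on the logit scale around 5.2%: 1.26–1.30 (equal), 1.54–1.68 (uneven).
- The same spread around 10.4% (twice 5.2%): 1.13–1.16 (equal), 1.27–1.35 (uneven).
- One clearly lowest discipline (1.5% against 6%): 1.02–1.11.

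**5. If the rule is re-applied in the elective and emergency subsets.** The two subsets get different references in 80–93% of studies with equal true risks (50/50 or 70/30 split), and in 67–81% when risks differ as in the first line of step 4 (60/40 split). The figure is 49% when the largest discipline is clearly lowest (60/40 split). In mix A at 5.2%, a subset of half the patients has an event-free reference in about 30% of studies.

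**The case against.** **Reference choice is only a parameterisation.** This is right for the model fit, the overall test of discipline and the other factors' odds ratios. It is not right for the 12 discipline odds ratios, intervals and p-values, which are what Table 3 prints.

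**Thirteen disciplines from cardiac to ophthalmology will not share one risk.** The SAP introduction itself lists type of surgery as a potential risk factor, and suggests that low- and middle-income countries may carry at least double the burden. This reduces the size. At 10.4% with differing risks the inflation is 1.13–1.35, and with one clearly lowest discipline it is close to nothing. It does not remove the bias, and the SAP names no such discipline.

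**The events-per-variable screen changes the adjusted model.** At 2.32% there are 0.0232 × 7000 = 162 events: 162/19 = 8.5 per variable or 162/40 = 4.1 per odds ratio, both below the SAP's limit of 10. At 5.2% the per-odds-ratio count is 364/40 = 9.1. If the screen is an overall test of discipline, the factor would enter in only about 5% of studies with no true differences. So the adjusted figures at 2.32% mostly describe a model that would not be fitted. The unadjusted column is reported regardless and remains affected.

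**The bound at 1 holds for crude odds ratios.** If the univariable column comes from the planned mixed model, hospital-conditional odds ratios are not bounded at 1. This stands; no hospital effect was simulated.

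**The SAP may mean one reference, chosen once, and does not say that the sensitivity analyses repeat Table 3.** That is a natural reading, so step 5 is conditional. The text leaves it open.

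**The effect is visible and the analysis exploratory.** Table 1 will show patients and events by discipline, and the SAP describes the model so: "Generalized mixed effects model analysis will be performed for exploration of candidate variables for prediction of risks for the primary outcome". Both are fair reasons not to rate this as a threat to the study.

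**Conclusion.** The concern holds. The reference is chosen by the outcome, and the discipline odds ratios are inflated together as a result. With 7000 patients and no true differences, the median unadjusted odds ratio is 1.28–1.81 with equal sizes and 1.50–2.03 with the assumed uneven sizes, against a true value of 1. With true differences the inflation is 1.13–1.68 across the rates and size mixes tried, falling to 1.02–1.11 if one discipline is clearly lowest.

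The small-reference and event-free risks depend on there being disciplines of roughly 70 patients, and the event-free risk is large only at the lowest cited rate. These sizes are assumptions, and the figures move with them and with the handling of zeros: another uneven mix (largest discipline 22%, three at 1%) with a 0.5 correction gave 2.95 / 1.70 / 1.50 at the three rates.

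The matter is confined to 12 odds ratios under a secondary objective. It should be corrected because the correction is simple and loses no information.

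**What to change.** Replace the sentence on the reference discipline with a rule that does not use the outcome: the discipline with the most patients in the full cohort, kept the same in the elective, emergency and country-exclusion analyses. Deviation-from-mean (sum-to-zero) coding is an alternative. Report one overall adjusted Wald or likelihood-ratio test for type of surgery before reading individual disciplines; the SAP already plans an unadjusted chi-squared or Fisher's exact test.

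The cost is one sentence and one reference entry in Table 3, with no new data. Odds ratios will then fall on either side of 1. A discipline with no events will still have an inestimable odds ratio of its own under a fixed reference, but the problem stays in that one contrast and does not spread to all 12. The SAP should say how such a discipline will be reported.

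### Case duration, which an intraoperative event can itself lengthen or shorten, sits in the Table 3 risk-factor model and can distort both its own odds ratio and that for severity of surgery

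*SAP*

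**What the plan says.** Secondary objective 2 of the SAP is: "To identify risk factors independently associated with severe critical events". Table 3 reports the results and is titled "Univariable and multivariable analysis of preoperative factors associated with intra-operative severe critical events". Within it, a block headed "Intraoperative factors" contains Duration and use of the surgical checklist, each with univariable and multivariable columns.

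SAP section D, item 2, sets the entry rule: "All variables will be entered into the model, unless there are less than 10 events per variable". If that condition fails, "risk factors with a p value ≤ 0.05 for severe critical events identified by univariate analysis will be entered into the model". Neither branch screens a variable on whether it precedes the outcome.

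SAP section B describes the modelling as "exploration of candidate variables for prediction of risks for the primary outcome". Under Sensitivity analyses the SAP states "Two sensitivity analyses will be conducted": one by elective and emergency surgery, the other excluding the two largest contributing countries. Neither drops duration.

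The SAP does not restrict duration to planned time or to time before the event.

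**The concern.** The outcomes in Table 2 (failed intubation, laryngospasm, cardiac arrest and so on) fall inside the interval that an end-of-case duration measures. Some events prolong the case, an abandoned procedure or a death shortens it, and others make no difference. Recorded duration may therefore be partly a consequence of the outcome.

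Two things follow. First, the duration odds ratio cannot be read as a risk-factor estimate, because exposure time and reverse causation are mixed. Second, conditioning on a variable that the outcome affects distorts the estimates for whatever else determines that variable, chiefly severity of surgery. Final duration is also unknown before surgery, so it does not suit the predictive purpose in SAP section B.

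The protocol does not supply a justification. Objective 3 in section 4.2 relates intraoperative factors to postoperative complications and death, which follow the operation. That ordering is lost when the outcome is itself intraoperative.

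**Working it through.** The documents give no assumed odds ratio for duration or severity, so there is no planned figure to reproduce. Two checks apply.

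**1. Can duration enter under the SAP's rule?**

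Coefficients in Table 3: age 1, sex 1, ASA 3, urgency 1, severity 2, indication 3, hospital level 2, surgeon 3, anaesthetist 3, type of surgery 12, comorbidities 6, duration 1, checklist 1, time of day 1. The total is 40 coefficients from 19 variables. The protocol summary gives 7000 patients (section 5.10 says there is no specific sample size). The event rates are those cited in the SAP introduction.

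| Event rate | Events (7000 × rate) | Per variable (÷19) | Per coefficient (÷40) |
|---|---|---|---|
| 2.32% | 162 | 8.5 | 4.1 |
| 5.2% | 364 | 19.2 | 9.1 |
| 11.7% | 819 | 43.1 | 20.5 |

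Either branch may apply, depending on the event rate and on how variables are counted. Under the first, duration is always in. Under the second, it enters if its univariable p is at most 0.05.

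**2. What does including it do?**

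Simulation, with all inputs except the event rate assumed:
- Severity minor/intermediate/major 45/40/15%, true odds ratios 1/1.6/2.5.
- High ASA 15%, odds ratio 2.0.
- Baseline duration D0 log-normal, medians 40/70/120 min, log-SD 0.5.
- Event rate 5.2%; 400,000 patients per scenario; z scaled to 7000.

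The event is drawn first: logit P = a + ln(1.6)·intermediate + ln(2.5)·major + ln(2)·highASA. Duration is then changed for the affected events, either by an exponential delay or by a uniform cut of 0 to 30 min (floor 5 min). The fitted model contains severity, ASA and duration in hours.

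| Effect of the event on duration | Major-surgery OR, duration in | Duration OR per hour | z |
|---|---|---|---|
| 30% of events add mean 10 min | 2.2 | 1.07 | 1.0 |
| 30% cut by up to 30 min | 3.0 | 0.87 | -1.8 |
| All add mean 10 min | 1.7 | 1.25 | 3.8 |
| All add mean 20 min | 1.2 | 1.50 | 7.3 |
| All add mean 30 min | 0.9 | 1.77 | 10.4 |
| All cut by up to 30 min | 5.0 | 0.58 | -5.9 |

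With duration left out, the major-surgery OR is about 2.5 in every row. Reruns agree within simulation error. At event rates of 2.32% and 11.7% the span is similar (0.9 to 4.9 and 0.8 to 5.2).

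Rough hand check: adjusted OR ≈ 2.5 ÷ (duration OR)^Δ, where Δ is the major-minus-minor difference in mean duration. The log-normal mean is the median × exp(0.5²/2) = median × 1.133, so Δ = (120 − 40) × 1.133 = 91 min = 1.51 h. The first two rows give 2.5 ÷ 1.07^1.51 = 2.3 and 2.5 ÷ 0.87^1.51 = 3.1, close to the simulated 2.2 and 3.0.

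The ASA odds ratio does not move unless ASA also drives duration. If high ASA lengthens cases by 25%, it falls from 2.0 to 1.8/1.7/1.6.

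**If duration truly matters** (assumed OR 1.3 per hour), the major-surgery OR is 3.8 without duration, a total effect. With duration it is 2.5 if events leave duration unchanged, but 1.3 (duration OR 1.80) if all events add a mean of 20 min.

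**A second simulation with different assumptions** (200 replicates of 7000; true major OR 2.25; no duration effect) gave 1.43 when each event adds 15 min and 5.76 when each cuts duration by 25%. Omitting duration gave 2.24 to 2.27. With no true effect of severity or duration, a 15-min prolongation put duration through the p ≤ 0.05 screen in 100% of replicates, against 6% when events left duration unchanged.

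**The case against.** The best counter-argument is about size. The extreme figures need every event to act on duration in one direction, whereas Table 2 mixes events as different as low glucose and cardiac arrest. With 30% of events affected, the 95% intervals at 7000 patients are about 1.6 to 3.2 and 2.1 to 4.2, and both contain 2.5. Opposing effects can also cancel: if 30% of events add a mean of 10 min and 20% are shortened by up to 30 min, the major-surgery OR is 2.5. The planned model is mixed-effects with many more terms, including type of surgery, which may itself explain duration. These points stand, and they make the figures illustrative. They do not remove the mechanism, and the net direction cannot be known from the documents.

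On the univariable screen, duration already has an OR of about 1.20 (z about 3.5) with no reverse causation, because severity drives duration. A pass is therefore not in itself evidence of reverse causation. The screen is still not a safeguard.

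The case record form is listed as a protocol appendix but not reproduced, so a definition of duration may exist there. Its absence is not held against the plan. Any definition that runs to the end of surgery or anaesthesia has the same problem.

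Finally, exposure time may be a genuine risk factor, and dropping it changes the severity estimand from a direct to a total effect. That is correct, and it is the reason to report both models and say what each estimates.

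**Conclusion.** The concern holds. As written, the plan can yield a duration odds ratio that is partly reverse-causal and a severity odds ratio biased in either direction. Table 3 also contradicts its own title. The mechanism follows from the timing of outcome and covariate and needs no numerical assumption.

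The size does rest on assumptions. Against a true 2.5, 2.2 to 3.0 represents a minority of events changing duration, and 0.9 to 5.0 is the span when all of them do. The reach is limited to secondary objective 2. The primary incidence result and Tables 1, 2 and S1 are untouched. It should be fixed before analysis.

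**What to change.** - Take Duration out of the main univariable and multivariable models in Table 3, and keep it as a descriptive row in Table 1.
- Add a third, labelled sensitivity analysis that refits the main model with duration, shown beside it, with a note that duration may be a consequence of the event.
- State that the severity odds ratio in the main model is a total effect, including any effect of longer exposure.
- Retitle Table 3 to match the rows kept, since checklist use also sits under the intraoperative heading.

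A planned or procedure-typical duration could replace the recorded one if such a variable exists; the documents do not show that it does.

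The cost is one row moved to a sensitivity table and a few lines of SAP text, with no new data. The main model will no longer separate severity from longer exposure, which is why the with-duration model is kept alongside it.
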